## 1. Introduction / Overview

The use of electronic cigarettes (e-cigs) is increasing rapidly. Yet, little is known about the potential lung toxicity for inhaling e-cig aerosols relative to smoking. The Food and Drug Administration (FDA) has deemed regulatory authority over e-cigs and needs data to determine how to regulate their designs and constituents. It is plausible that e-cig aerosol constituents (carriers, flavor, and byproducts of these) induce an inflammatory response in the lung, but there is no direct evidence for this, and what the magnitude of the effect is, if any. While there may be numerous ongoing laboratory *in vitro* and *in vivo* studies to assess e-cig exposure and toxicity, these utilize indirect methods for assessing lung toxicity. There also are ongoing human studies that focus on the effect of e-cig use on smoking-related biomarkers of exposure, but these usually assess biofluids outside the lung (e.g., blood and urine). It is unknown how any of these studies may relate to lung toxicity, i.e., the target organ, and thus there is a critical research gap. To assess human lung toxicity from e-cig use, we propose to conduct a clinical trial of 128 smokers to assess inflammatory responses in the lung via serial bronchoscopy. To do this, we will exploit an extraordinary opportunity for study e-cig toxicity by employing a new standardized research e-cig (SREC), a recently developed e-cig by the National Institute on Drug Abuse (NIDA) that will be submitted to the FDA for use as an investigational tobacco product. (This protocol is a NIDA-funded study, and OSU was only one of 3 groups nationally selected to investigate this product.) The study will also utilize a design that will allow for continual recruitment of control subjects with the potential to add new arms/conditions as novel products enter the market. This protocol may be amended as new products become available. This design will facilitate timely and cost-efficient investigation. In the current iteration, subjects will be randomized to continued cigarette smoking (control), one of two e-cig use conditions (complete substitution with the nicotine-SREC or placebo-SREC), or complete substitution with nicotine replacement therapy (NRT). Each group will be 32 subjects and the trial will be 10 weeks (a 2 week run-in period, followed by 8 weeks of the experimental condition). Primary outcomes will be lung biomarkers (cell counts and inflammatory cell subtypes, altered macrophage phenotypes such as lipid-laden macrophages, inflammatory cytokines, exhaled nitric oxide, mRNA and microRNA gene expression, DNA methylation, acrolein DNA adducts, proteomics, and mitochondrial DNA mutations and copy number variation, lipidomics, gene methylation, microbiomes, nicotine and carcinogen metabolites, CyTOF, proteomics, propylene glycol and glycerin, and untargeted metabolomics). Pulmonary function tests also will be assessed. Several biochemical measures to assess compliance will be employed (e.g., exhaled Carbon monoxide (CO) level, urinary tobacco alkaloids, nicotelline, nicotine boost, propylene glycol and glycerin). A biorepository of urine, blood and nasal samples will be created for future studies to compare non-invasive biomarkers with lung biomarkers. The infrastructure for this trial that investigates the pulmonary effects of e-cig use among non-smokers is already established under an FDA- and OSU IRB approved protocol (OSU-2015C0088; Clinicaltrials.gov NCT02596685), which has completed more than 100 bronchoscopies. This study is significant because it will focus on lung inflammation, a plausible effect on the lungs of e-cig use, and the impact for switching to e-cigs, versus complete cessation with NRT. Such data are needed as soon as possible to assist the FDA in the regulation of e-cigs, including nicotine content. It also will provide critical data to NIDA about the use of their product and smoking behavior for other studies they intend to fund in the future. The study is innovative by using a clinical trial design using serial bronchoscopy, incorporating inflammation biomarkers with metabolomic and gene expression data, and uses an integrative, complementary and comprehensive approach through multiple 'omics assays. It also is innovative because it will provide unique data for the effects of nicotine on the human lung for inflammation and other pathways. This study has considerable public health impact because it will provide experimental evidence in humans of target organ effects.

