We propose to assess pulmonary effects of e-cig use in a randomized clinical trial of 128 smokers, some of whom will be provided e-cigs, such as the SREC, for 10 weeks (2 weeks run-in period and 8 weeks of the experimental condition) assessing biomarkers obtained by bronchoscopy (bronchoalveolar lavage [BAL] and lung brushings). Participants will be randomized to one of four groups of subjects (n=32 for each group): a control group who will continue to smoke their usual brand, a group who will switch completely to the SREC with nicotine, a group who will switch completely to the SREC placebo and a group who will stop smoking using nicotine replacement therapy (NRT). Using serial bronchoscopy, we will assess pulmonary inflammatory biomarkers and 'omics to provide direct evidence of the effects of e-cigs, with and without nicotine, compared to continued smoking and complete cessation. Using bronchoscopies at baseline and after 8 weeks of the experimental condition (after a 2 week run-in period), the primary outcomes will be a change in inflammatory cell counts and inflammatory cell subtypes, altered macrophage phenotypes such as lipid-laden macrophages, inflammatory cytokines, fractional exhaled nitric oxide (FeNO), mRNA and microRNA (miRNA) gene expression, gene methylation, DNA methylation, acrolein DNA adducts, proteomics, and mitochondrial DNA mutations and copy number variation, lipidomics, microbiomes, nicotine and carcinogen metabolites, CyTOF, proteomics, propylene glycol and glycerin, and untargeted metabolomics. Pulmonary function tests (PFTs) also will be conducted.

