Summary for the effects of combustible cigarette smoking on the human lung: Numerous studies have implicated changes related to inflammatory responses related to smoking. Critical pieces of evidence include the demonstration of differences between smokers and non-smokers, a dose-response with smoking, and reversal of changes with cessation. Given that there is sufficient evidence overall to consider that smoking has an effect on inflammation, it is reasonable to consider that other inhalational exposures also will induce an inflammatory response.

We are planning to conduct a 10 week trial on product (2 week run in period and 8 week intervention). The rationale for this duration balances data showing reversibility for many of the above markers within 4-6 weeks versus a potential concern for retention of smokers in a trial for longer periods of time using an untested product; SREC acceptability to smokers is unknown. Although a longer trial might reveal additional e-cig related changes, 8 weeks should be sufficient to provide meaningful data because, as summarized above: 1) it is known that lung inflammation following infection usually reverses by 6 weeks detected radiographically; and 2) sputum macrophages decrease within 1 week [70], FeNO decreases to normal within 4-6 weeks [69, 71], neutrophils decrease within 6 weeks studies [68, 69], and many gene expression associations reverses within three month of cessation [49]. For this study, we will monitor inflammatory cell counts in real time for each of the groups to assess reduction in cell counts.

Viral exposure precautions: As COVID-19 or other viral illnesses persist, study procedures have been updated to adhere to institutional standards and best practices. Given the situation continues to evolve, study procedures may also adapt to address subject and personnel safety as well as study and institutional resources. For example, the study may be temporarily suspended if there is significant community spread and resources (e.g., bronchoscopy staff or space) are limited. Similarly, as vaccination uptake increases or if scientific evidence demonstrates prolonged immunity after exposure, testing prior to procedures may not be necessary. Regardless, staff will implement sufficient precautions to mitigate viral exposure. Such precautions may include limiting

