**Randomization:** At the baseline bronchoscopy visit, subjects will be randomized before the procedure to one of the 4 groups (control and interventions). Those assigned to receive an intervention, will receive the product for free. All intervention groups will receive motivational counseling for smoking cessation. Study staff will be blinded regarding study groups. Medical personnel will be informed if she/he deems it pertinent or if the subject is assigned to receive the placebo and varenicline.

**Standardized Research Electronic Cigarette:** This study will utilize the NIDA SREC, which was developed under contract to NJOY (<https://www.drugabuse.gov/funding/supplemental-information-nida-e-cig>) so that it can receive Investigational Tobacco Product (ITP) designation for this study (<https://www.fda.gov/TobaccoProducts/Labeling/RulesRegulationsGuidance/ucm463951.htm>). The purpose of the ITP is for the FDA to allow for the study of tobacco products without pre-market evaluations that are required for medications and devices. Under current federal law, tobacco products that are not already on the market may be permitted by the FDA for research studies. With this application, NJOY will submit a master file that includes premarket data that the FDA will assess prior to determining the ITP status. Concurrent with this protocol, an ITP application also has been submitted. This application has already been reviewed and approved by NIDA. Without an ITP, NIDA will not allow the SREC product to be provided for use.

The FDA process to assess a product as an ITP, the FDA generally considers whether there are controls on how and to whom the tobacco products intended for investigational use are distributed; whether the protocol for the clinical investigation or the procedures used during the clinical investigation adequately provide for the protection of human subjects; whether the study is designed to ensure the quality and integrity of the study data and permit other investigators to replicate the findings; and, whether there are adequate procedures in place to ensure that investigational tobacco products are not commercialized.

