Subjects who indicate difficulty maintaining a reliable source of communication (i.e., telephone, internet access) after enrolling in the study may be provided a cell phone to facilitate communication, data collection via internet, and improve retention. The cell phone and a data plan may be provided at no cost to the participant. Subjects will be instructed to return the phone at the end of the study. Phones will be erased and reused as needed. No data from the phone will be captured or retained.

**Day 15/ Wk 2, Day 22/ Wk 3, Day 29/ Wk4, Day 43/ Wk6 and Day 57/ Wk 8 visits (+/- 3 days):** Subjects in the intervention arms will begin their assignment (stop smoking) effective on day 15. Subjects will be offered the opportunity to complete the questionnaires online and measure their breath CO within 24 hours before each scheduled visit. At each visit, blood pressure, heart rate, oxygen level and weight will be recorded. Subjects will complete questionnaires. CO will be assessed. Subjects in the intervention groups will be asked to bring back their used and unused product and will be provided additional pods, varenicline and NRT as appropriate. Subjects who fail to return product or report daily use may be identified as non-compliant and removed from the study by the PI on a case by case basis. At day 57/Wk 8 visit, subjects will be given 24 hour urine collection containers and instructions. Subjects will receive a reminder to begin 24-hour urine collection the day before their bronchoscopy.

**Follow-up bronchoscopy:** At 10-weeks (8 weeks on the experimental condition and a 2 weeks run-in period), subjects randomized to the SREC groups will be instructed to use the assigned device immediately prior to the visit. During the visit, these subjects will demonstrate use and inhalation will be assessed in a closed room with negative pressure or a “smoke eater” device that will reduce the exposure to exhaled particles. Windows or webcams may be utilized to observe and communicate with participants during this exercise. No webcam images or audio data will be recorded or retained without the participants’ permission.

Inhalation of the SREC will be assessed by the Great Lakes Neurotechnology BioRadio System, which includes

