- 2) Descriptive statistics and clustering (e.g., principal components analysis [PCA]), will be performed for all biomarker data measured at the different visits. Baseline data (1st bronchoscopy) will then be compared between the four groups (3 conditions and control) using a one-way analysis of variance (ANOVA). The non-parametric Kruskal-Wallis test (continuous or ordinal variables) or the chi-square test (categorical variables) will be applied when the normality assumption of the data is not met. We will compare controls to complete substitution with the SREC (with and without nicotine) or NRT. Generalized linear models (GLM) will be employed with measurement (cell count, gene expression, etc.) as the dependent variable, a covariable for baseline measure, and a main effect of arm. Other relevant variables that are associated with the biomarker results, e.g., baseline smoking, Fagerstrom Test for Nicotine Dependence (FTND), or gender will also be included in our models as they are potential confounders. We also will assess batch effects and include batch as a co-variable in the model (all samples will be analyzed at the same time, except for cell counts). We plan to use baseline molecular measurement as a covariable rather than

modeling the change between baseline and follow-up because the former is more powerful [1]. Given the large dynamic range of the cell count and the 'omics data, we will initially consider a normal distribution. If the data are determined to deviate from normality, we will log-transform the data or assume a non-normal distribution of residuals (such as Poisson) for the GLM. Urine propylene glycol (PG) will be measured at the 2nd bronchoscopy visit and compared to baseline to verify e-cig use. As an exploratory analysis, urinary PG will be used as the exposure predictor variable assessing the biomarker results as dependent variables. Urine anatabine, urine anabasine and nicotelline will be used to confirm complete substitution or a predictor variable for smoking reduction. The cotinine level will be used as a surrogate for smoking reduction.

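### Cell counts, a primary outcome, are to be monitored by arm in real time, which conflicts with blinded study staff; no one is named to see them and no limit is set on their use

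*Protocol*

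**What the plan says.** The paragraph of Protocol section 3 that justifies the 2-week run-in and 8-week intervention closes with the plan that "we will monitor inflammatory cell counts in real time for each of the groups to assess reduction in cell counts". It gives no viewer, frequency, masking or decision rule.

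Protocol section 2 puts cell counts at the head of its list: "the primary outcomes will be a change in inflammatory cell counts and inflammatory cell subtypes". Section 4.g.ii uses them for the sample size. SAP item 2 states that "all samples will be analyzed at the same time, except for cell counts" (section 4.g.i has the same exception), so counts arrive while the trial is running.

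On blinding, the Randomization paragraph of section 4.c.i says "Study staff will be blinded regarding study groups". Section 4.d.v also blinds the laboratory personnel who run the assays. Section 4.a.iii plans a Data and Safety Monitoring Board.

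On conduct, the paragraph on the Day 15 to Day 57 visits says "Subjects who fail to return product or report daily use may be identified as non-compliant" and may be "removed from the study by the PI on a case by case basis". Section 1 says "This protocol may be amended as new products become available", and section 4.a.ii lets the arms on offer vary with product availability. SAP item 1 gives up intention-to-treat for follow-up outcomes, because participants who do not finish have no second sample.

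**The concern.** A count cannot be summarised for each group without the group codes. If study staff do the monitoring, the blinding statement fails. If someone else does it, the plan does not say who.

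This matters because several decisions in the same period are left to judgement: whether to enforce the non-compliance rule, how hard to work to retain a participant, and whether to continue or amend. A team that knows how each arm is trending on a primary outcome can be influenced in these decisions without intending it. The analysis has no intention-to-treat backstop, and only about 21 participants per arm are expected at follow-up, so a handful of such decisions could carry weight.

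**Working it through.** **Plan's own figure.** Inputs from section 4.g.ii and SAP item 1: 32 enrolled per group and 66% retention. 32 × 0.66 = 21.12, rounded down to 21 per group; 21 × 4 = 84. Both match the documents.

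**Who could do by-arm monitoring?**
- Section 3 requires counts for each group, in real time.
- Section 4.c.i blinds study staff, and section 4.d.v blinds assay personnel. Neither can do it and stay blinded.
- Section 4.a.ii has a biostatistician supervise randomization, and section 4.a.iii plans a board. Neither is assigned this monitoring.
- Sections 4.f.ii, 4.f.iv, 4.f.v and 4.h refer participant safety monitoring, adverse events, premature removal and the monitoring plan to an attached document that was not available here.

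The two statements therefore conflict unless an unnamed third party does the work.

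**Could removal select on a participant's own result?** Tables 2 and 3 and section 4.e.iii place lavage samples at Day 1 and about Day 71 only. The discretionary removal rule sits in the Day 15 to Day 57 paragraph. At that point the participant has a baseline count and no follow-up count, so selection on that person's own follow-up count is not possible by this route.

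Selection on the baseline count is possible, but SAP item 3 (Model 1) adjusts for baseline. A simulation under no effect started with 21 per arm, removed the 1, 2 or 3 highest baseline counts from one arm, and assumed baseline to follow-up correlations of 0.3, 0.5 and 0.7. The baseline-adjusted test stayed close to its nominal 5% throughout. What remains is the softer route: arm-level trends, built from participants who have already finished, colouring decisions about those still enrolled.

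**What would unadjusted looks cost?** The documents give no number of looks, no interim test and no stopping rule, so all of these are assumptions. Simulated for one comparison with no effect, up to 21 per arm, stopping at the first two-sided t-test result below 0.05:

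| Looks (number per arm) | False-positive rate |
|---|---|
| One (21) | 5.1% |
| Four (6, 11, 16, 21) | 12.2% |
| Seventeen (every step from 5 to 21) | 19.1% |

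The planning threshold for cell counts is 0.0001, not 0.05. With a z-test at that level, two looks (11, 21) give about 0.0002, four looks (5, 11, 16, 21) about 0.0003 and seventeen about 0.0007. These figures show how repeated looks with stopping behave. They are not error rates of this plan.

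**The case against.** The strongest reply is that nothing improper is planned. The SAP specifies one follow-up comparison. Removal has stated triggers, namely failing to return product or to report daily use. Arm changes are tied to product availability and to formal amendment. Past changes have external reasons on record: the longer intervention was made to harmonize with other grantees at the funder's request, and the revision history ties the earlier added arms to newly available commercial devices. Counting cells as samples arrive may be a practical necessity and does not imply by-arm access. The monitoring plan that was not available may already restrict access.

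Most of this stands. It rules out three stronger readings that a reader might infer:

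- That the investigator could remove the participants with the highest follow-up counts. The visit schedule excludes this under the stated rule.
- That the false-positive rate is 12% or 19%. The plan contains neither the tests nor the stopping that those figures need.
- That arms have been or will be changed in response to results. No passage links the counts to arms, removal, duration or stopping.

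The reply does not remove the conflict between sections 3 and 4.c.i, or the lack of an access rule in the protocol text and SAP. If the monitoring plan has such a rule, section 3 should cite it. The blinding statement is also thin protection on its own: staff dispense pods, varenicline and nicotine replacement and counsel the intervention arms only, so visit staff could often infer the arm.

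**Conclusion.** The point holds as an internal conflict with an unprotected access path. The protocol states a practice that exposes a primary outcome by arm during the trial, says elsewhere that study staff are blinded, and in the documents supplied neither names who sees the counts nor limits their use. The risk is that arm-level trends influence enforcement, retention effort, or decisions to continue or amend, in an analysis that drops participants without follow-up.

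Its size cannot be stated. No interim test or decision rule exists to attach an error rate to, and the simulated figures rest wholly on assumed looks. The conclusion also assumes that the separate monitoring plan does not already settle access. This is a cheap improvement, not a flaw that invalidates the design.

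**What to change.** Replace the monitoring sentence in Protocol section 3 with:

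> Incoming cell counts are reviewed by study staff only pooled over arms, for sample quality. Any by-arm summary is prepared by a statistician not involved in removals, retention or arm decisions and goes only to the DSMB. Outside DSMB safety review, by-arm counts are not used to change duration, arms or sample size, or to remove participants.

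Then reconcile this text with the blinding statement in section 4.c.i and with the data safety monitoring plan, citing any access rule already there. The safety exception is needed so that the board can still act on a signal of lung inflammation.

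The cost is a few lines of text. Sample size, visits and assays do not change, and a board and a biostatistician are already in the plan, although that biostatistician can prepare the summaries only if not involved in the decisions listed. The downside is that investigators do not see early trends by arm.

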***Nicotine is a highly bioactive agent that inhibits inflammation:*** This study will include an assessment of the SREC with and without nicotine. Nicotine content can be regulated by the FDA and some considerations for this will be affected by the addictiveness (abuse liability) of the product, but toxicity considerations may also apply. It is well established that nicotine is highly bioactive in that it induces proliferation, inhibits apoptosis, promotes the epithelial to mesenchymal transition (EMT), and promotes angiogenesis [257, 258]. All of these are important components of cancer and COPD [219, 257]. To date, nicotine is not considered a significant carcinogen for humans as nicotine replacement therapy or in low-TSNA smokeless tobacco (snus) have not demonstrated increased risks of cancer [259]. Regarding inflammation, nicotine is both pro- and anti-inflammatory, and therefore theoretically able to affect cancer and COPD pathogenesis in different ways [258, 260-265]. In cell culture studies of human bronchial epithelial cells, while cigarette smoke condensate increases inflammatory cytokine production, nicotine does not, and pretreatment with nicotine reduced the condensate effects [261]. In a study of wound healing in smokers, compared to continued smoking and quitting with or without nicotine, it was observed that the nicotine replacement therapy (NRT) reduced inflammation and macrophage infiltration, but not angiogenesis [260]. In human nasal epithelial cells, in contrast to cigarette smoke and acrolein, nicotine induced inflammatory cytokine response [266]. *In vivo*, nicotine was able to inhibit acute lung injury in mice through anti-inflammatory effects [265]. The anti-inflammatory effect may be through the stimulation of nicotinic receptors present in lung and other cells, and there are data that nicotinic receptor agonists reduce acute lung injury [262, 267, 268]. There are nicotinic receptors on macrophages that reduces pro-inflammatory cytokines while having no effect on anti-inflammatory cytokines [269]. In contrast to data for nicotine reducing inflammation, other data, using different experimental models, indicate that nicotine may increase inflammatory response because of its toxic effects on the lung epithelium [210, 216]. Pro-inflammatory effects have been observed in cell culture models of vascular smooth muscles and in atherogenesis, because it can induce oxidative damage [270, 271]. In contrast to the above cited studies, some data indicate that nicotinic receptors increase inflammation in human lung and decreases lung function [267]. Because of the potential anti-inflammatory effect of nicotine, it has been tested if NRT can be used as a treatment for inflammatory disease, such as ulcerative colitis, but the results have been inconclusive to date [264, 272]. In this application, we will test the SREC with and without nicotine providing a unique opportunity to assess nicotine effects on the lung in the context of e-cig aerosol exposure, an important research gap [219]. For the purposes of this study, our hypothesis is that nicotine will attenuate an e-cig aerosol inflammatory response because most of the data supports a greater anti-inflammatory effect and human studies do not indicate that NRT is a carcinogen. Future studies may consider exposures in humans with e-cigs having differing levels of nicotine, but the first step to demonstrate an effect by nicotine would be the comparison for the most extreme difference, i.e., with and without nicotine, as proposed herein.

***Summary of Significance:*** This study is significant in the following ways:

- This study will directly assess the inflammatory response of the SREC aerosols in the human lung for smokers who use e-cigs for 8-week on-product experimental condition, compared to continued smoking or

quitting with NRT. The lung is an important target organ for smoking-related disease, i.e., cancer and lung disease.

- The focus on smokers is particularly significant in that about 50% of smokers are known to have tried e-cigs and about 23% of smokers have switched to e-cigs as cessation devices, and will compare the reduction in inflammation compared to known and effective ways to quit smoking [3-6]. This data is relevant for informing smokers about their choice of how to quit smoking.
- Nicotine content and delivery can be regulated by the FDA. The pulmonary effects of nicotine inhalation are essentially unknown, but it is plausible that it has an effect because it is a highly bioactive molecule. The SRECs provide a unique opportunity to provide data for the magnitude of such an effect, if any.
- This study will use the SREC. It was developed by NIDA because of an important research gap regarding e-cig toxicity, where essentially no two commercial e-cigs are alike, and their product performance and toxicant yields are generally unknown. These likely differ among the diverse products on the market. Also, commercial products frequently change in their marketing and performance without notice (e.g., a product may be withdrawn from the market) making ongoing studies problematic. These issues are addressed by the NIDA's development of the SREC, and long term availability.
- Assessing the SREC's effect on pulmonary toxicity allows for the comparison of studies conducted by other investigators who also use the SREC in both human and preclinical studies.
- In addition to examining SREC, this study may examine the effects of other devices, such as Juul and IQOS (and potentially other novel products) on pulmonary toxicity.
- The proposed application will establish the feasibility for use of the SREC for clinical trials using bronchoscopy, and provide baseline data to design future studies of commercial e-cigs.
- This study will utilize biomarkers of diverse physiological responses, all relating to inflammation, namely combining gene expression, metabolism, cell infiltrates and inflammatory cytokines. Importantly, the multi-omic approach will allow us to examine other disease pathways, including those affected by nicotine.
- The infrastructure for conducting e-cig and smoking-related bronchoscopy studies is established. Our preliminary data indicates that we can accomplish this study (see below). The OSU IRB protocol is approved to conduct serial bronchoscopies in healthy never smokers trained to use nicotine- and flavor-free e-cigs (OSU-2015C0088; Clinicaltrials.gov NCT02596685) and accrual is going briskly. We also have a separate infrastructure to conduct multi-arm randomized trials for smoking behavior and biomarkers (OSU-2013C0015; Clinicaltrials.gov NCT01867242).
- This study will include a biorepository of urine, blood, saliva, lung and nasal samples for future studies to compare non-invasive biomarkers with lung biomarkers.
- This study was funded by application responding to NIDA PAR-17-156: Evaluating the NIDA Standardized Research E-Cigarette in Risk Reduction and Related Studies (U01) because we are studying the health effects of e-cig aerosols in the human lung using the SREC. The research objective for the PAR was: "This FOA will encourage short studies that can be completed within a shorter time frame. Applications submitted to this FOA should use subjects who are current smokers and investigators should use the NIDA SREC in their studies." The PAR specifically encourages the following research: "Health effects associated with changes in toxin exposure as a result of SREC use compared with conventional smoked tobacco". It also will provide data for: "The ability of conventional smoked tobacco users to switch to the nicotine-containing or placebo SREC and the impact on health risk endpoints." Our application was only one of 3 studies funded by NIDA with an impact score of 17.

[figure not shown]
